1. INFORMATION FROM THE STUDY PROTOCOLS

1.1. Introduction

1.1.1. Introduction

According to American Cancer Society statistics non-Hodgkin's Lymphoma (NHL) is the most prevalent hematopoietic neoplasm, representing approximately 4% of all cancer diagnoses in men and women and ranking seventh in frequency among all cancers. Since the early 1970s, the incidence rates of NHL have nearly doubled. Lymphoma includes a heterogeneous group of malignancies originating from lymphoid tissues (mainly of lymph nodes) with different biology and prognoses divided into 2 large groups of neoplasms: (1) non-Hodgkin's lymphoma and (2) Hodgkin's disease. Various neoplastic tumor cell lines correspond to each of the cellular components of antigen-stimulated lymphoid follicles. Almost 85% of NHLs are of B-cell origin.

NHL includes many clinicopathologic subtypes, each with a distinct epidemiology; etiology morphology, immunophenotype, genetic features, clinical characteristics and response to therapy. For many of the B-cell NHL subtypes, the pattern of growth and cell size may be important determinants of tumor aggressiveness.

MT-3724 is a single polypeptide chain consisting of 512 amino acids and a recombinant homodimeric fusion protein. Each monomer consists of a single chain variable fragment (scFv) with affinity for human CD20 cell surface protein fused to the enzymatically active Shiga-like toxin-I A1 subunit (SLT-I A1). MT-3724 has not yet been given to human subjects.

The main study, a Phase I, multiple ascending dose study will seek to enroll subjects with progressive B-cell NHL with measurable disease (lesion > 1.5 cm) who have received standard treatment with at least one anti-CD20 antibody containing front-line regimen that resulted in initial response, followed by relapse/recurrence and who are not eligible for any further approved biologic therapy, chemotherapy and/or autologous stem transplantation and/or refuse alternative approved therapies and/or are unlikely to achieve clinical benefit from any therapy of higher priority by Investigator assessment. The extended access, compassionate use study is available only to those subjects who have successfully completed the MT-3724 NHL main study and require continued treatment for their NHL.

1.2. Study Objectives

This statistical analysis plan (SAP) contains detailed information on definitions of analysis populations, derived variables, and statistical methods for the analysis of safety and efficacy data from the Phase I/ Ib clinical studies: MT-3724_NHL_001_US and MT-3724_NHL_001_EXT_US. The statistical analyses and summary tabulations described in this SAP will provide the basis for the results sections of the clinical study report (CSR) for this trial. This SAP will also outline any differences in the currently planned analytical objectives relative to those planned in the study protocol.

The SAP is based upon the following study documents:

- Study protocols v7.0 dated 08 February 2018 for MT-3724_NHL_001_US and v2.0 dated 16 April 2016 for MT-3724_NHL_001_EXT_US.
- Electronic Case Report Form (eCRF), v10.0 dated 16 May 2018.

Although Part 1 of this study allows for the enrollment of subjects with NHL or Chronic Lymphocytic Leukemia (CLL), at the time of writing this SAP there are no plans to enroll subjects with CLL, as Part 1 of this study is complete. No subject with CLL were enrolled in Part 1.

1.2.1. Main Study

1.2.1.1. Primary Objectives

In Part 1, subjects with NHL or CLL were enrolled, and the primary objectives were:

- To define the maximum tolerated dose (MTD) of a single course of MT-3724 given on Days 1, 3, 5, 8, 10 and 12 at which there are negligible side effects (adverse events) and/or at which maximum pharmacokinetic (PK)/pharmacodynamic (PDn) parameter changes are observed.
 - The MTD was determined to be 75 mcg/kg/dose. However, due to safety concerns, an adjusted MTD (50 mcg/kg/dose) is used for Part 2.
- To determine PK and PDn profiles of a single course of MT-3724 in escalating dose cohorts.

In Part 2, up to 40 additional subjects with relapsed/refractory diffuse large B-cell lymphoma (DLBCL) will be treated with the adjusted MTD (50 mcg/kg/dose) of MT-3724 in the MTD expansion cohort. The primary objectives will be to:

- Identify the frequency and nature of clinical and laboratory adverse events (AEs), both reported and observed, as a measure of safety and tolerability over repeated cycles of MT-3724 at the adjusted MTD.
- Define the PK and PD profiles of MT-3724 at the adjusted MTD in this sub-population.

1.2.1.2. Secondary Objectives

For Part 1, the secondary objectives are as follows:

- To identify the frequency and nature of clinical and laboratory adverse events, both reported and observed, as a measure of safety and tolerability over repeated courses of MT-3724.
- To assess the PK and PDn over repeated courses of MT-3724 from Day 1 though 112.
- To assess the efficacy of MT-3724 in subjects with DLBCL.

1.2.1.3. Exploratory Objectives

The exploratory objectives for Parts 1 & 2 are as follows:

1.2.2. Extension Study

1.2.2.1. Primary Objectives

The primary objectives of this study are as follows:

- To provide extended access to MT-3724 on a compassionate use basis for subjects who require continued treatment for their NHL or CLL and have (1) tolerated MT-3724 throughout the MT-3724_NHL_001_US Phase I/Ib study (Core and Repeat Dosing), (2) maintained stable disease or better and (3) have no other acceptable and better treatment options available to them in the Investigator's judgment.
- To identify the frequency and nature of clinical and laboratory adverse events, both reported and observed, as a measure of safety and tolerability over repeated cycles of MT-3724 beyond those administered in the MT-3724_NHL_001_US Phase I/Ib study.

1.2.2.2. Exploratory Objectives

The exploratory objectives of this study are the following:

1.3. Study Design

1.3.1. Synopsis of Study Design

1.3.1.1. Main Study

This is an open-label, phase 1/1b, dose-escalation study of MT-3724. There are two parts to this study, which include Part 1: Evaluating doses of MT-3724 in subjects with relapsed, refractory B-cell NHL or CLL to determine the MTD; and Part 2 (implemented in version 6.0 of the study protocol): The MTD cohort was expanded to evaluate safety, tolerability, and potential efficacy at the MTD. Implemented in version 7.0 of the study protocol, up to 40 additional subjects with DLBCL will be treated with MT-3724 at the adjusted MTD (50 mcg/kg/dose).

Part 1: The first 12-day course of treatment will be followed by at least 16 days of observation to provide a 28-day safety assessment following initiation of dosing. Each additional treatment cycle will be at least 21 days in length. In Part I, the first treatment cycle is 28 days (Core Study). All subsequent cycles (Cycles 2 – 5, Repeat Dosing Study) will be 21-day cycles. Subjects may receive up to 5 total cycles in the absence of clear disease progression or toxicity. If a subject achieves complete remission (CR), post Cycle 2, then 2 additional cycles will be attempted, after which dosing may be suspended.

Part 2: Each treatment cycle will be at least 21 days in length. Subjects may receive up to 5 total cycles in the absence of clear disease progression or toxicity

Parts 1 and 2: Retreatment under a separate extension protocol will be considered for subjects who exhibit PR or SD after completing 5 cycles (or 2 cycles after a complete remission) in consultation with the Sponsor.

Schematics of Parts 1 & 2 of the main study is presented in Figures 1 and 2.

Figure 1: Part 1 Study Schematic

[figure not shown]
[figure not shown]

Figure 2: Part 2 (MTD Expansion) Study Schematic

Core Study (Cycle 1, Days 1 to 28)

Subjects will receive a single course of study drug via a 2 to 4 hour intravenous (IV) infusion of MT-3724 on Days 1, 3, 5, 8, 10 and 12. The first dosing cohort will receive 5 micrograms per kilogram (mcg/kg) per dose of MT-3724. Each cohort is planned to have from 3 to 6 subjects, but additional subjects may be added to one or more dosing cohorts to further explore safety and/or efficacy signals. Following the first dose in the Core Study, there will be a minimum 28-day observation period for each subject to document safety and tolerability prior to initiating any additional treatment cycles in the Repeat Dosing Study (see below). Subjects experiencing a dose limiting toxicity (DLT) in the Core Study (Days 1-28) must be withdrawn from the study and receive no further doses of MT-3724. Subjects will have successfully completed the Core Study if they receive at least 4 of the 6 infusions in their first cycle and they are followed for 28 days after their first dose. If a subject in the Core Study completes less than 4 of the 6 infusions in the first 12 days and the missed infusions were not due to an MT-3724-related DLT or AE that contraindicates further dosing then the Investigator in consultation with the Sponsor may attempt to achieve a minimum 4 infusions by administering the missed doses in the third week (Days 15 - 19) of the Core Study. In such instances, subjects must still be observed for 28 days following the first dose in the Core Study prior to initiating any further study drug dosing.

Following Data Monitoring Committee (DMC) safety review and approval to escalate, the subsequent cohorts are planned to be dosed at 10, 20, 50, 100, 150, and 200 mcg/kg/dose.

- **Dose Escalation:** Additional dose cohorts may be added above the 200 mcg/kg/dose cohort if (1) less than two DLTs are observed at the completion of that cohort's first cycle and (2) maximum PK/PD parameter changes have not yet been observed. The incremental increases of cohorts beyond 200 mcg/kg/dose/day will be determined by the PK/PD observations and all safety data.
- **Dose-De-escalation:** Additional cohorts at dose levels below an identified toxic dose level will be added to more accurately identify the MTD. At the identification of the first dose cohort that has > 33% DLTs, the maximal administered dose, an interim cohort will be added at a dose that is approximately 25 mcg/kg/dose lower than the maximal administered dose. If that lower dose has > 33% DLTs then the next highest cohort by a further 25 mcg/kg/dose reduction will be studied. For example, if there are > 33% DLTs at the 150 mcg/kg/dose, it will become the maximal administered dose and a 125 mcg/kg/dose cohort will be added. If the 125 mcg/kg/dose cohort has > 33% DLTs then the next lowest dose cohort (100 mcg/kg/dose in this example) will be expanded to 6 subjects if not previously done. Cohorts will be explored at ~25 mcg/kg/dose reductions until the MTD has been identified by documenting < 33% DLTs in a cohort expanded to the required 6 subjects. If the MTD cohort identified in the Core Study is expanded beyond 6 subjects for further PK, PD and/or efficacy exploration then from their first cycle, the subjects added to this expansion cohort will be dosed according to the Repeat Dosing 21-day cycle.

Part 1 Repeat Dosing (Cycles 2-5)

Following successful completion of the 28-day Core Study of Part 1, subjects may continue to receive up to 4 more cycles of treatment as long as they have experienced no AE attributable to MT-3724, which would contraindicate further dosing and provided their disease has not progressed.

If a subject has tolerated repeat cycles of MT-3724 without evidence of a toxicity that would prohibit further dosing or evidence of disease progression, but their dose is subsequently determined to be above the MTD, he/she may continue to receive additional cycles at the highest studied dose in Part 1 that has been confirmed to be below the MTD or at the dose confirmed to be the MTD.

Part 2

Up to 40 subjects will be enrolled in Part 2. Subjects may be enrolled and treated simultaneously through competitive enrollment at multiple study centers in North America and Europe.

All subjects will receive a single course of study drug via a 2 (\pm 15 minutes) IV infusion of MT-3724 on Days 1, 3, 5, 8, 10 and 12. Each dose of MT-3724 will be at the adjusted MTD (50 mcg/kg/dose). Three subjects were started in Part 2 at 75 mcg/kg/day but later had possibly related TEAEs that required dose reduction or a treatment discontinuation. Following the first dose in each cycle, there will be a minimum 21-day observation period for each subject prior to initiating the next treatment cycle. Subjects experiencing a serious adverse event (SAE) attributable to MT-3724 may be withdrawn from the study or depending upon the nature of the

event, the Investigator, in consultation with the DMC, may, once the event has resolved, resume dosing at a dose reduced by 25-33%. Subjects will have successfully completed a cycle if they receive at least 4 of the 6 infusions in that cycle, and they are followed for 21 days after their first dose in that cycle. If a subject completes less than 4 of the 6 infusions in the first 12 days of a cycle and the missed infusions were not due to an event that would contraindicate further dosing, then the Investigator in consultation with the Sponsor may attempt to achieve a minimum of 4 infusions by administering the missed doses in the third week (Days 15 - 19) of that cycle. In such instances, subjects must still be observed for a minimum of 21 days following the first dose in Cycle 1 prior to initiating any further study drug dosing. No dose escalation will be permitted above the adjusted MTD (50 mcg/kg/dose) identified by the DMC. However, at the Investigator's discretion, the dose for any subject in the Part 2 expansion cohort may be reduced by 25-33% for one or more doses in any cycle (see below) based upon a subject's response at the adjusted MTD (50 mcg/kg/dose).

Subjects must receive a minimum of 4 of the 6 infusions in a cycle in order to successfully complete that cycle and continue in the study. For subjects in Parts 1 and 2 who complete **at least 4** of the 6 infusions in any cycle, and the missed infusions were not due to an MT-3724-related event that contraindicates further dosing (see above for criteria for continued dosing), then up to 5 total cycles may be administered on the same schedule (Days 1, 3, 5, 8, 10 and 12) and at the same dose (as long as that dose is not subsequently identified to be a toxic dose).

If the adjusted MTD (50 mcg/kg) is determined to be causing adverse effects for a subject, at the Investigator's discretion, that subject may continue to receive additional cycles at a dose that is 25-33% lower than the adjusted MTD.

For both Parts 1 & 2, subjects in any cohort who complete **less than 4** of the 6 infusions in any cycle and the missed infusions were not due to an MT-3724-related AE that would contraindicate further dosing, the Investigator (in consultation with the Sponsor) may attempt to achieve a minimum of 4 infusions by administering the missed dose(s) in the third week (Days 15-19) of the cycle. In such instances, subjects must still be observed for at least 21 days after their first dose in one cycle prior to initiating their next cycle in Part 1, repeat dosing cycles, or Part 2, all cycles.

Long Term Safety Follow-up

Following the Final Safety Assessment, subjects will be contacted by telephone every 6 months from the date of their first dose for up to 2 years or until they initiate further treatment for their B-cell NHL, CLL, or other malignancies or take any other investigational new drug for any reason. Subjects will be asked about their current medical status and if they have experienced any new AE attributable to their MT-3724 treatment. If the subject continues to participate in the MT 3724 extension study, no AEs will be captured with respect to long-term safety within this parent study, as they will be captured in the extension study.

[figure not shown]

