subject enrolls in this study prior to the identification of the MTD in the Core Study, the subject must continue at their originally assigned dose (mcg/kg) until the MTD is identified. If a subject has tolerated repeat cycles of MT-3724 without evidence of (i) a toxicity that would prohibit further dosing or (ii) disease progression, but their dose is subsequently determined to be above the MTD, they may continue to receive additional cycles at the highest studied dose that has been confirmed to be below the MTD or at the dose confirmed to be the MTD. Following the successful completion of a treatment cycle in this extended access study, subjects are eligible to receive the next cycle (to a maximum of 6 cycles) as long as (i) they have experienced no AE attributable to MT-3724 which contraindicates further dosing AND (ii) their disease has not progressed. For subjects in any dosing cohort who complete less than 4 of the 6 infusions in a cycle, and the missed infusions were not due to an MT-3724 related AE that would contraindicate further dosing then the Investigator may attempt to achieve a minimum of 4 infusions by administering the missed doses in the third week of that dosing cycle. In such an instance, for that cycle only, at the Investigator's discretion and in consultation with the Medical Monitor, a subject may be observed for less than 9 days prior to initiating their next cycle.

Long Term Safety Follow-up (Extension)

Following the assessment performed 14 - 28 days after the last MT-3724 dose in this study, subjects will be contacted by telephone every 6 months from the date of their first dose in the MT-3724_NHL_001_US Core Study for up to 2 years OR until they initiate further treatment for their B-cell Non-Hodgkin's Lymphoma (NHL) or B-cell Chronic Lymphocytic Leukemia (CLL) OR until they take any other investigational new drug for any reason. During these telephone contacts subjects will be asked about their current medical status and if they have experienced any new AE attributable to their MT-3724 treatment.

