1.3.5.2. Efficacy Parameters

As this is a dose finding study and is designed to assess the safety and tolerability of MT-3724, all efficacy analyses are exploratory in nature, based on documented tumor responses.

Tumor response following completion of even numbered (e.g., 2, 4, etc.) courses of MT-3724 and at final safety assessment following termination of MT-3724 will be assessed according to the Tumor Response Criteria for malignant lymphoma ([Cheson et al 2007](#)) defined by the International Working Group.

In addition, source document verified tumor lesion measurement data that was not reported in the EDC was collected and tallied by the Sponsor via an Excel Spreadsheet. The data in this Spreadsheet will be used for the analysis of percent change in tumor size.

Endpoints will include:

- Best Overall Response.
- Objective response rate (ORR) - Objective response will be determined as the proportion of subjects with either CR or PR using the tumor response criteria described below.
- Disease Control Rate (DCR) will be calculated as the proportion of subjects who achieve either CR, PR or stable disease status.
- Duration of tumor response (DOR) - Duration of response is defined as the time from the first occurrence of either complete or partial response to first documented evidence of disease recurrence or progression. Subjects without evidence of progression will be censored at time of last disease assessment. Only responders (CR or PR) will be included for this analysis.
- Progression-free survival (PFS) – Progression-free survival is calculated from the date of first infusion of MT-3724 to first documented evidence of disease recurrence or progression or death due to any cause. Subjects who are last known to be alive and without evidence of progression will be censored at time of last disease assessment.
- Duration of stable disease (i.e., duration of disease control) - Duration of at least stable disease is defined as the time from the date of first infusion of MT-3724 to first

documented radiologic evidence of disease recurrence or progression. Subjects without evidence of progression will be censored at time of last disease assessment.

- Overall survival (OS) – Overall survival is calculated from the date first dose of study treatment to the date of death. Subjects who are still alive prior to the data cutoff for final efficacy analysis, or who dropout prior to study end, will be censored at the day they were last known to be alive.

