3.2. General Methods

All data listings that contain an evaluation date will contain a relative study day (Rel Day). Pre-treatment and on-treatment study days are numbered relative to the day of the first dose of study medication which is designated as Day 1. The preceding day is Day -1, the day before that is Day -2, etc.

All output will be incorporated into Rich Text Format (RTF) files, sorted and labeled according to the International Conference on Harmonisation (ICH) recommendations, and formatted to the appropriate page size(s).

Tabulations will be produced for appropriate demographic, baseline, efficacy, and safety parameters. For categorical variables, summary tabulations of the number and percentage of subjects within each category (with a category for missing data) of the parameter will be presented. For continuous variables, the number of subjects, mean, median, standard deviation (Std Dev), minimum, and maximum values will be presented. Time-to-event data will be summarized using Kaplan-Meier methodology using 25th, 50th (median), and 75th percentiles with associated 2-sided 95% confidence intervals (CIs), as well as percentage of censored observations.

This study is primarily descriptive in nature; therefore, there are no formal statistical hypothesis tests planned. Hypothesis testing may be employed if warranted.

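### In the SAP studies, follow-up contact ends at the next anticancer treatment, so the planned Kaplan-Meier curve is not overall survival as the SAP defines it, and the direction of bias is unknown

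*SAP*

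**What the plan says.** The SAP covers the main study (Parts 1 and 2) and the Extension.

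- **Contact, main study** (SAP 1.3.1.1, Long Term Safety Follow-up). Subjects are telephoned every 6 months from first dose "for up to 2 years or until they initiate further treatment for their B-cell NHL, CLL, or other malignancies", or until they take another investigational drug. The content of the call is also given: "Subjects will be asked about their current medical status and if they have experienced any new AE attributable to their MT-3724 treatment".
- **Contact, Extension** (SAP 1.3.1.2). The schedule is the same. Calls end at 2 years, at further NHL or CLL treatment, "OR until they take any other investigational new drug for any reason".
- **OS** (SAP 1.3.5.2). "Overall survival is calculated from the date first dose of study treatment to the date of death". Subjects alive at the data cutoff, "or who dropout prior to study end, will be censored at the day they were last known to be alive". New therapy is neither an event nor a named reason for censoring.
- **Method** (SAP 3.2). Time-to-event data get Kaplan-Meier 25th, 50th and 75th percentiles with 95% confidence intervals and the percentage censored.
- **Status.** SAP 1.3.5.2 says "all efficacy analyses are exploratory in nature, based on documented tumor responses", and SAP 3.2 says "there are no formal statistical hypothesis tests planned".

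The assessment schedules in SAP 1.3.4 have no survival row, and the SAP mentions no search of records for vital status.

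**The concern.** The endpoint needs every death, whatever treatment came before it. The contact rule stops looking at the moment many subjects with relapsed lymphoma move on. Under SAP 1.3.1.1, further cycles are allowed only without clear disease progression, so progression ends study treatment and is a natural trigger for new therapy. A subject who makes that move leaves the risk set alive, and any later death is recorded only if the site happens to learn of it.

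Kaplan-Meier treats censored subjects as having the same future risk as those still under observation. That is doubtful when censoring follows progression and also depends on being fit enough for more treatment. The resulting table would carry the label overall survival while describing something else. It would also not be comparable with OS from Parts 3 and 4, where Protocol 4.1.3 and 8.1.5 keep collecting deaths after progression.

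**Working it through.** The SAP gives no event count, power or expected value for OS, so there is no planned figure to reproduce. The check sets the rules against each other and then asks how large the effect could be, and in which direction.

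**1. The rules together.** Take a subject who progresses, starts new lymphoma therapy and dies later. The contact rule ends the calls at the new therapy. The OS rule censors at the last date known alive. Followed as written, the plan counts this subject as a censored survivor. A subject who progresses, is too ill for more treatment and dies stays in contact and is counted as a death. Whether a death is seen thus depends on whether next therapy was started.

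**2. Simulation: progression, then next therapy.** All inputs are assumptions, because the documents give no next-therapy rates:

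- exponential time to progression, median 2 or 3 months;
- exponential survival after progression, median 4 or 6 months, the same for treated and untreated subjects;
- next therapy one month after progression in 30%, 50% or 70% of those still alive;
- administrative end at 24 months.

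The true curve uses all deaths; the plan's curve censors at next therapy. As a check on the first row below, with a = ln2/2 = 0.3466 and b = ln2/4 = 0.1733, true survival is S(t) = (a·e^(−bt) − b·e^(−at))/(a − b). At t = 7.1 this is 2 × 0.292 − 0.085 = 0.499, so the true median is about 7.1 months.

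| Progression / post-progression median (months) | Share treated | True median OS | Kaplan-Meier under the plan | Difference |
|---|---|---|---|---|
| 2 / 4 | 30% | 7.1 | 7.5 | +0.4 |
| 3 / 4 | 50% | 8.4 | 9.8 | +1.4 |
| 3 / 6 | 70% | 10.7 | 13.5 | +2.8 |

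The first and last rows are the extremes of the 12 settings. Across all of them, follow-up stopped alive in 25% to 62% of subjects, and about the same share of deaths within 24 months went unseen.

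**3. Same model, fitter subjects receive next therapy.** Post-progression survival now differs by receipt of therapy.

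| Progression median (months) | Post-progression median, treated / untreated | Share treated | True median OS | Kaplan-Meier under the plan |
|---|---|---|---|---|
| 2 | 8 / 2 | 50% | 7.0 | 6.3 |
| 2 | 6 / 3 | 50% | 7.3 | about 7.3 |
| 3 | 6 / 3 | 70% | 9.4 | about 10.7 |

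The bias can be downward, near zero or upward.

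**4. Closed-form check with a different structure.** Let the death hazard be h before next therapy and r·h after it. Next therapy starts at hazard a, so the share starting it is p = a/(a + h). Then h is set so that true median OS is 6.3 months. That is the OS figure Protocol 2.1.3 cites from a retrospective study in refractory DLBCL, taken here as a median. Kaplan-Meier censored at next therapy estimates e^(−ht), with median ln2/h.

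Worked case, p = 50%, r = 2: a = h, so S(t) = e^(−2ht)(1 + ht). With h = 0.0910, S(6.3) = 0.318 × 1.573 = 0.50. The Kaplan-Meier median is 0.693/0.0910 = 7.6 months.

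| r | p = 30% | p = 50% | p = 70% |
|---|---|---|---|
| 0.5 | 5.8 | 5.2 | 4.3 |
| 1 | 6.3 | 6.3 | 6.3 |
| 2 | 7.0 | 7.6 | 8.7 |
| 3 | 7.4 | 8.5 | 10.3 |

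Deaths are lost whatever the direction. For 40 subjects (the Part 2 maximum, SAP 3.1) at p = 50% and r = 2, deaths by 24 months number 40 × (1 − S(24)) = 38.4. Those seen before next therapy number 40 × 0.5 × (1 − e^(−0.182 × 24)) = 19.7. At r = 1 there is no bias, but 17 of 37 deaths still go unseen.

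**The case against.** The strongest reply has four parts.

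1. **The calls are safety calls.** The text says when they stop; it does not say that a death date learned later is discarded, and "will be censored at the day they were last known to be alive" would allow its use. This is right as far as it goes. A reader might infer that deaths after new therapy are excluded by rule; the SAP does not say so. What stands is that no planned route collects them, and informal capture would be uneven.

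2. **The visible text is incomplete.** Part of SAP 4.3 does not appear in the public copy, and main-study protocol v7.0, on which the SAP rests, is not among the documents. OS handling could be described there. This lowers confidence, but it does not reconcile the contact rule and the OS definition that are visible.

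3. **The direction is not established.** A reader might infer that reported OS must be too favourable, because progressors leave the risk set. Sections 3 and 4 of the working show reversal when recipients of next therapy are fitter or have a lower hazard afterwards. Protocol 2.1.3 itself links response to survival, especially in patients able to go on to stem cell therapy. This objection stands in full.

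4. **Little depends on it.** OS is exploratory and untested, Part 1 cohorts are planned at 3 to 6 subjects, and Part 2 has at most 40. This also stands and limits the weight of the point.

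The better follow-up in Protocol 4.1.3, 7.4 and 8.1.5 is not an answer, because it applies to Parts 3 and 4.

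**Conclusion.** The point holds for Parts 1 and 2 and the Extension. The SAP defines OS to death but shows no contact that would find deaths after next-line therapy, and it summarises the result with a method that needs censoring unrelated to prognosis. The curve is therefore not OS as defined.

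Its size cannot be fixed from the documents. Under the assumptions shown, the median is about 0.4 to 2.8 months too long when next therapy is unrelated to prognosis, and about 0.7 months too short in the fitter-recipient example (6.3 against 7.0). Both models censor exactly at the start of next therapy; with calls 6 months apart, the real last-known-alive dates would be coarser.

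Two wider readings are not supported. A reader might extend the point to Parts 3 and 4, but subjects who discontinue there for progression are followed for OS, and the calls collect both death and new therapy. A reader might also think a formal conclusion is at risk, but no test, alpha or sample size depends on this endpoint.

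**What to change.** State in SAP 1.3.5.2 that OS uses survival status regardless of any new therapy. For subjects whose calls ended at new therapy or another investigational drug, obtain the death date or latest date known alive through a one-time query to sites.

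If that cannot be done, report how many subjects were censored at new therapy and label the estimate as survival censored at start of next therapy, not as OS. A cumulative incidence of death before next therapy, with next therapy as a competing event, is an optional addition.

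The cost is a short query for a small cohort (an estimated 20 to 40 subjects in Part 1 and at most 40 in Part 2) and a few lines of SAP text, or only relabelling and a count. OS may look less favourable once the missing deaths are included. No treatment or assessment rule changes.
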